The human macula has a high concentration of the dietary carotenoids lutein and zeaxanthin which results in a yellow spot centered on the fovea, the *macula lutea*. Carotenoids are abundant in plants, fruits, and vegetables, and they are thought to play important roles in the physiologic function of the retina and other tissues (Scott et al., 1996; Scarmo et al., 2010; Zimmer et al., 2007; [name] et al., 2016). Of the hundreds of carotenoids found in nature, 10 to 15 are detectable in human serum, but only lutein, zeaxanthin, and their metabolites are present in the retina (Bone et al., 1985; Khachik et al., 1997). The potential antioxidant and photoprotective effects of carotenoids, especially with regard to age-related macular degeneration (AMD), have been studied extensively in the laboratory and in clinical studies (Seddon et al., 1994; [name] et al., 2002; Eye Disease Case-Control Study Group, 1993), and recent reports have demonstrated a role of dietary and supplemental carotenoids in slowing or preventing AMD (Age-Related Eye Disease Study (AREDS) Report No. 22, 2007; AREDS2 Report No. 3, 2014).

Studies also suggest a functional role for the macular carotenoid pigment earlier in life, at a time when they may enhance contrast sensitivity, decrease glare disability, and even increase visual acuity (Kvansakul et al., 2006; Stringham et al., 2008; Olmedilla et al., 2003). The physiological accumulation of the macular carotenoid pigments occurs even *in utero* (Malone, 1975; Dimentstein et al., 1996). Investigators have recently shown that the macular pigment is detectable immediately after birth, correlates with infant and maternal serum zeaxanthin levels, and progressively increases through the first seven years of life ([name] et al., 2013). This suggests that the macular carotenoids play physiological and protective roles throughout the lifecycle and may be particularly important during infant visual development.

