Initial evaluation of each mother's carotenoid status will be obtained prior to starting any study supplements. Subsequent evaluations while participants are taking the study supplements will be performed in conjunction with routine prenatal visits to their Obstetrician, at approximately 22-26 weeks gestational age and again at 37-39 weeks gestational age. All mothers will undergo a final assessment within two weeks of giving birth.

Infants' evaluations will be performed in the first two weeks of life, either during the original hospital stay or at a follow up outpatient clinic visit.

Visit:	Screening/ Baseline	Maternal Supplementation		
	T1	T2	T3	Birth
Timeframe:	Before 14 Wks GA	22-26 Wks GA	37-39 Wks GA	0 to 2 Wks
Informed Consent	X			
Randomization	X			
Maternal visual acuity and contrast sensitivity	X	X	X	X
Maternal nutritional surveys	X	X	X	X
Dilated eye examination	X			
Maternal serum carotenoids	X	X	X	X
Maternal macular pigment imaging	X	X	X	X
Maternal skin carotenoids	X	X	X	X
Dispense prenatal supplement and do pill counts	X	X	X	X
Infant cord blood carotenoids				X
Infant macular pigment imaging				X
Infant foveal imaging (sdOCT)				X
Infant skin carotenoids				X

Unscheduled Visits

Mothers may be seen for Unscheduled Visits if deemed necessary for repeat measurements or follow-up of Adverse Events. If a mother delivers her baby prematurely, she and her infant will remain in the study and will be asked to complete the final study visit.

Description of Study Assessments:

Visual Function - Manifest refraction, and measurement of best-corrected visual acuity and contrast sensitivity of the mothers will be obtained by certified ophthalmic technicians using standardized protocols. The study staff performing visual acuity will be masked to the treatment assignment. Best-corrected visual acuity testing will be assessed on ETDRS back-lit charts starting at a distance of 4 m, and should precede any examination requiring administration of eye drops to dilate the eye or any examination requiring contact with the eye. Contrast sensitivity will be measured by the Pelli-Robson threshold contrast sensitivity chart at 1 m.

Maternal Eye Exam - The complete ophthalmic exam will consist of the following:

- External examination of the eye and adnexa.
- Routine screening for eyelids/pupil responsiveness (including ptosis, abnormal pupil shape, unequal pupils, abnormal reaction to light and afferent pupillary defect).

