Maternal Macular Pigment Levels - Mothers' macular pigment will be measured using the dual wavelength autofluorescence method which measures attenuation of lipofuscin autofluorescence by blue absorbing macular pigment. The subject looks at a fixation target with her dilated study eye for about 30 seconds as her macula is scanned sequentially with alternating 486 nm (blue) and 518 nm (green) lasers, and autofluorescence images are collected. Macular pigment images are prepared by digitally subtracting the green image from the blue image using appropriate correction factors to compensate for the absorption spectrum of the macular carotenoid pigment and then analyzed using macular pigment analysis software after setting the zero point at 9 degrees of eccentricity. This instrument and software has proven to be highly reliable and reproducible, especially when measuring macular pigment volume under the curve at 9 degrees.

Serum Carotenoid Levels - Blood samples obtained from mothers and from infant cord blood will be analyzed for serum carotenoid content using well-established laboratory protocols that can provide baseline separations of all common dietary carotenoids. Whenever possible blood samples will be obtained by piggy backing onto a routine clinical blood collection.

Dietary Questionnaires - At each study visit mothers will be asked to complete the LZQ quantitative food frequency questionnaire that captures ~90% of the lutein/zeaxanthin foods consumed in the US, based on National Health and Nutrition Examination Survey data.

Safety Evaluations - Any clinically significant abnormalities persisting at the end of the study/ early withdrawal will be followed by the investigator until resolution or until a clinically stable endpoint is reached. The study includes procedures to monitor safety, including complete Ophthalmic exams and monitoring of adverse events.

Optional Specimen Collection and Banking Sub-Study

Participants will be asked to allow a sample of placenta tissue to be collected and stored for future research related to maternal to infant carotenoid transport on a tissue level.

Participants will be asked to provide a saliva sample to be stored and used for future research related to the genetics of carotenoid metabolism enzymes.

Participants will be asked to allow a portion of their blood collected at study visits to be stored for future research related to the genetics of carotenoid metabolism.

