Statistical power and sample size (N) for one of the primary outcome measures, maternal skin carotenoids at birth, was determined using data from the previous study by Henriksen et al. (2013) in which the average maternal skin carotenoids \pm SD at birth was 34000 ± 8300 . This value is 20% lower than the University of Utah Moran Eye Center clinic average value of $\sim 42,500$ Raman counts reported for the ancillary AREDS2 study ([name] et al., 2012). With power of 0.90 and alpha 0.05, a sample size of 20 was calculated for each group in order to detect and prevent a 20% decline during pregnancy. In order to accommodate subsequent ineligibility due to premature birth, low birth weight, or other problems ($\sim 10\%$) and to plan for expected noncompliance and loss to follow up ($\sim 20\%$), we intend to enroll 30 subjects in the Carotenoid Supplementation Group and another 30 in the Control Group.

The other outcome measures (maternal ocular carotenoid depletion during pregnancy, infant carotenoid status at birth, and the exploratory outcome measures of foveal maturity at birth and visual function changes during pregnancy) are not as well characterized, but we estimate that a similar sample size of 20 patients per group will be sufficient to detect differences in these indices.

Statistical Analysis Sets

The Intent-to-Treat set will include all randomized subjects who complete the Baseline Visit carotenoid status evaluations and receive study supplements. Subjects will be analyzed by the supplement arm assigned at the Baseline Visit.

A modified Intent-to-Treat set will include all randomized subjects who receive investigational product and complete carotenoid evaluations for at least one trimester study visit while utilizing study supplements.

Efficacy Analyses

The primary, secondary and exploratory efficacy analyses will be performed using the modified Intent-to-Treat subject set. Paired t-tests will compare the carotenoid status at enrollment and at the final study visit of the mothers receiving carotenoid supplementation to mothers not receiving carotenoid supplementation. We will also compare carotenoid status of infants whose mothers received carotenoid supplementation to infants of mothers without carotenoid supplementation. Significance will be set at 2-tailed $P < 0.05$. The associations between maternal and infant carotenoid status will be assessed with regression analysis.

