Other or additional details (specify):

6. **How often is study data and documentation monitoring planned (e.g., monthly, twice a year, annually, after N participants are enrolled, etc.)?**

Data monitoring will occur every 3 months.

Title: Lutein & Zeaxanthin in Pregnancy (L-ZIP) - Carotenoid Supplementation During Pregnancy: Ocular and Systemic Effects

6. Risks and Benefits

1. Describe the reasonable foreseeable risks or discomforts to the participants:

Risks of Carotenoid and Control Supplements – Both kinds of supplements are within the standard of care expectant mothers would receive if they were not in the study. They pose no additional risk to participants.

Risks of Visual acuity and contrast sensitivity – These are routine vision tests and pose no risk to participants above standard medical care.

Risks of Ophthalmic imaging – Light levels projected on the retina during the photographs and macular pigment measurements are well within established safety limits. Participants may notice a central dark spot in their vision similar to the afterimage generated by a camera flash. This will fade in about 5 minutes. Infants may experience discomfort during the macular pigment imaging and foveal imaging. Parents may feel emotional distress when observing the infant undergoing this safe examination.

Risks of Carotenoid skin measurements – There are no expected risks from the light exposure from the skin measurement. It is important not to look directly at the laser for a long period of time.

Risks of Blood draws – Whenever possible the blood samples for this study will be taken at the same time participants are having blood drawn for routine prenatal blood work. The blood sample from the infants umbilical cord will be taken at the same time blood is collected for his/her routine care.

Risks of Eye exams – The dilation drops used for the exams are considered standard of care for dilated eye exams during pregnancy.

Risks of Nutrition surveys and supplement logs – recording diet and supplement intake will take a few minutes of participants time, but poses no risk.

Risks of genetic research and sample banking - There is a potential risk of loss of confidentiality, but procedures are in place to make this highly unlikely.

Unforeseeable Risks - In addition to the risks listed above, participants may experience a previously unknown risk of side effect.

2. Describe the potential benefits to society AND to participants (do not include compensation):

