Title: Lutein & Zeaxanthin in Pregnancy (L-ZIP) - Carotenoid Supplementation During Pregnancy: Ocular and Systemic Effects

Investigational Drug Data Form

- 1. Name of Investigational Drug:** Lutein-2mg Zeaxanthin Softgels
- 2. Synonyms:**
Softgel containing 10 mg lutein, 2 mg zeaxanthin, and safflower oil.
- 3. Manufacturer or Other Source:** Kemin Health, Des Moines, IA
- 4. Other Study Drugs:**
Placebo softgel (Kemin Health) containing safflower oil (control group will receive).
Prenatal vitamins (all participants will receive)
- 5. Type of Study (Blinding Information):**
Double-masked
- 6. Strength(s) and Dosage Form(s):**
The active study supplement, Kemin Health Lutein-2mg Zeaxanthin softgel, is a commercially available, over the counter product containing 10 mg of lutein and 2 mg zeaxanthin per softgel.
- 7. Indications for Use and Pharmacology:**
Nutritional supplement
- 8. Possible Side-Effects/Adverse Reactions:**
Kemin Health softgels with Lutein/zeaxanthin are within the standard of care expectant mothers would receive if they were not in the study. There are no expected physical risks associated with the supplements.
- 9. Drug Administration Information**
 - a. Usual Therapeutic Dose:**
1 softgel per day (10 mg lutein, 2 mg zeaxanthin)
 - b. Dosage Range:**
1 softgel per day
 - c. Therapeutic Blood Levels:**
unknown (not routinely tested in standard care)
 - d. Route of Administration:**
Oral
 - e. Rate of Administration for IV Infusion or Push:**
N/A
 - f. Reconstitution Directions (include stability info):**
N/A
 - g. Precautions and Special Instructions for Administration:**
During pregnancy and lactation take one softgel daily with food.
 - h. Toxicology and Antidote:**
There are no known toxic effects of taking too much zeaxanthin. Very large doses of carotenoids such as lutein and zeaxanthin can cause carotenodermia - a yellow-orange skin discoloration. It can look like jaundice, but the abnormal skin color can be removed with an alcohol swab. In case of

overdose do not induce vomiting. Contact Poison Control, physician or pharmacist for advice.

10. Describe the plan to control, store, and dispense the investigational drug. This plan should ensure that the drug is only used by qualified investigator(s) for the participants enrolled in this research project.

The Kemin softgels will be stored in and dispensed by the Moran Eye Center Pharmacy.

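### Infant skin carotenoids, macular pigment and sdOCT are labelled as at-birth outcomes but may be measured at any age from 0 to 14 days, and the comparison by arm names no adjustment for age at measurement

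*Combined protocol and SAP*

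**What the plan says.** All references are to the combined protocol and SAP.

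- **Timing.** Section 4, item 6 (Study Visit Schedule): "Infants' evaluations will be performed in the first two weeks of life, either during the original hospital stay or at a follow up outpatient clinic". Infant skin carotenoids, macular pigment imaging and sdOCT all fall in the Birth column, defined there as 0 to 2 weeks.
- **Label.** Section 4, item 9 (Sample Size Calculation and Power Considerations) lists "infant carotenoid status at birth, and the exploratory outcome measures of foveal maturity at birth".
- **Infant serum.** Item 6 (Serum Carotenoid Levels): "Blood samples obtained from mothers and from infant cord blood will be analyzed for serum carotenoid content". Section 6, item 1 adds: "The blood sample from the infants umbilical cord will be taken at the same time blood is collected for his/her routine care".
- **Comparison.** Item 9 (Efficacy Analyses): "We will also compare carotenoid status of infants whose mothers received carotenoid supplementation to infants of mothers without carotenoid supplementation". No covariate is named. The subgroup paragraph lists infant gender and an open-ended category of other factors. It does not list age at measurement, gestational age or feeding.
- **Dosing period.** The title and the primary objective concern supplementation in pregnancy. The Investigational Drug Data Form, item 9g, reads: "During pregnancy and lactation take one softgel daily with food". The schedule row "Dispense prenatal supplement and do pill counts" is marked at all four visits, including Birth. No section gives an end date for dosing.

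**The concern.** Three infant outcomes carry a label that fixes them at delivery, while the schedule lets one infant be measured on day 0 and another on day 14. The protocol itself suggests that age matters. The Background says that macular pigment "progressively increases through the first seven years of life", and that these carotenoids concentrate in eye and neural tissue before birth, above all in the third trimester. Preterm infants stay in the study under item 6, which widens the range of postmenstrual age at imaging. An unadjusted comparison leaves all of this spread in the error term, in groups planned at about 20.

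A second, separate matter is interpretation. If some mothers were still taking study softgels after delivery and were breast-feeding, an infant measured late could have had postnatal intake that differs by arm. The documents neither establish this nor rule it out, and feeding is not among the listed data, so it could not be examined afterwards.

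**Working it through.** **1. The plan's own figure.** The only calculated sample size is for maternal skin carotenoids; the infant outcomes borrow it. Inputs from item 9: means 34,000 and 42,500 (difference 8,500), SD 8,300, power 0.90, two-sided alpha 0.05.

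n per group = 2 × [8,300 × (1.960 + 1.282) / 8,500]² = 20.04.

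This agrees with the stated 20. The standardized effect is 8,500 / 8,300 = 1.02, and power at 20 per group is 89.9% (normal approximation). No effect size or SD is given for any infant outcome.

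**2. Which outcomes the window touches.**

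| Infant outcome | When fixed | Exposed to the 0–14 day window |
|---|---|---|
| Cord-blood carotenoids | Delivery | No |
| Skin carotenoids | Day of assessment | Yes |
| Macular pigment | Day of assessment | Yes |
| Foveal anatomy (sdOCT) | Day of assessment | Yes |

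**3. Age spread as noise.** Let R² be the share of outcome variance explained by age at measurement. The documents give no value, so 10% to 30% is assumed for illustration.

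- Residual SD ratio after adjustment = √(1 − R²): √0.90 = 0.949 and √0.70 = 0.837.
- Unadjusted group size giving the same precision as 20 adjusted infants = 20 / (1 − R²): 20 / 0.90 = 22.2 and 20 / 0.70 = 28.6.
- Seen from the other side, suppose the borrowed effect of 1.02 SD applied at a fixed age and the age variance were left in. The effect becomes 1.02 × √(1 − R²), that is 0.97 and 0.86, and power at 20 per group falls from 89.9% to 86.7% and 77.3%.

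Two cautions apply. The R² covers postnatal and gestational age together, and gestational age would add variance even if every infant were seen on day 0, so the window accounts for only part of the range. The small cost of estimating one slope is ignored.

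**4. Possible intake through milk.** Suppose no prenatal effect and an assumed between-arm postnatal gain of b SD per day. The spurious difference is d = b × mean age, and the rejection probability with 20 per group is Φ(d/√(2/20) − 1.96) + Φ(−d/√(2/20) − 1.96).

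| b (SD per day, assumed) | Mean age 2 days | Mean age 7 days |
|---|---|---|
| 0.01 | 5.0% | 5.6% |
| 0.05 | 6.2% | 19.8% |
| 0.10 | 9.7% | 60.0% |

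The results run from no effect to a large one. Neither b nor the age distribution is in the documents, so the table shows only that the size cannot be determined from them.

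**The case against.** A reader might infer more than the documents support, in four ways.

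- **That the whole infant comparison is confounded.** It is not. Cord blood is fixed at delivery and gives a clean comparison for prenatal transfer.
- **That age and maturation bias the result.** The trial is randomized and double-masked, so age at measurement balances in expectation. What remains is variance and chance imbalance. For foveal maturity, an exploratory outcome, the issue is mainly variance.
- **That mothers are dosed after delivery.** The schedule row combines dispensing with pill counts, so its mark at Birth may mean only the count. Supplement handed out at that visit could not affect measurements taken at the same visit. Item 9g is general administration wording on a drug data form. The end of dosing is undefined; post-delivery dosing is not shown.
- **That milk intake would favour the supplemented arm.** This needs continued dosing, breast-feeding, late measurement and sufficient uptake within days. None of these is established.

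It can also be said that the label may simply mean the visit named Birth, that no section limits the infant question to transfer before birth, that a rise in macular pigment over seven years says little about 14 days, and that the complete SAP is still to be finalized before database lock. These points lower the priority. They do not remove the gap: the stated comparison is unadjusted, and a later SAP cannot use feeding data that were never collected.

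**Conclusion.** The point holds in a limited form. Infant skin carotenoids, macular pigment and sdOCT may be measured anywhere from day 0 to day 14 under an at-birth label, and the plan names no adjustment for age. The expected consequence is lost precision and chance imbalance. On an assumed R² of 10% to 30%, adjusting would be worth about 22 to 29 infants per group in place of 20. That range is illustrative, and part of it belongs to gestational age. It also assumes that masked scheduling keeps age at assessment unrelated to arm. Retained preterm infants would widen the spread; the sample-size paragraph, however, allows for ineligibility after premature birth, so how many enter the analysis is unclear.

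Arm-differential intake through milk is an open question, not a finding, and its size cannot be derived from the documents. The primary outcome is maternal and foveal maturity is exploratory, so this is a cheap improvement of modest priority.

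**What to change.** 1. Name cord-blood lutein plus zeaxanthin as the lead infant measure of prenatal transfer.
2. For infant skin carotenoids, macular pigment and sdOCT, compare arms with postnatal age at measurement as a prespecified covariate, using postmenstrual age for foveal maturity. Both follow from dates the trial already holds.
3. Record feeding since birth. Because it arises after randomization, use it only for description or in a sensitivity analysis. Add a sensitivity analysis limited to infants measured within a fixed number of days of birth, with the cut-off set before unmasking. A cut by hospital stay would not serve, since preterm infants may stay longer and age would not be capped.
4. Reconcile the title and primary objective, the visit schedule and item 9g of the Investigational Drug Data Form on the period of maternal dosing. No dosing rule is proposed here.

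Cost: one covariate, one extra data item and one sensitivity analysis on a smaller subset. No new procedure is needed, and the SAP is not yet final.

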Study Protocol and Statistical Analysis Plan for NCT03750968

Lutein & Zeaxanthin in Pregnancy – Carotenoid Supplementation during Pregnancy: Ocular and Systemic Effects

The following pages contain the IRB approved study protocol and statistical analysis plan at the most recent renewal approved on 21 December 2022.

Date: Tuesday, May 2, 2023 2:01:03 PM

[Print](#)
[Close](#)
IRB_00116610
Created: 10/1/2018 12:13 PM

IRB_00116610

1. Contacts and Title

PI: [name]

Submitted: 11/21/2018

Title: Lutein & Zeaxanthin in Pregnancy (L-ZIP) - Carotenoid Supplementation During Pregnancy: Ocular and Systemic Effects

1. Study Introduction

1. Responsible Investigator:

[name]

Email	Training	Col Date
[contact]	7/27/2021 MCG	4/3/2023

a. Position of the Investigator:

- Faculty or Non-Academic Equivalent
- Student
- Staff
- Resident/Fellow
- Other

2. Contact Persons for the Responsible Investigator:

Name	Email	Training
[name]	[contact]	1/30/2023 MCG
[name]	[contact]	CG
[name]	[contact]	1/31/2023 MCG
[name]	[contact]	1/4/2023 MCG
[name]	[contact]	6/17/2022 MCG

3. Guests of the Responsible Investigator:

Last Name	First Name	E-Mail
-----------	------------	--------

There are no items to display

4. What type of application is being submitted?

[New Study Application](#) (or Amendment/Continuing Review)

5. Title Of Study:

Lutein & Zeaxanthin in Pregnancy (L-ZIP) - Carotenoid Supplementation During Pregnancy: Ocular and Systemic Effects

6. Study Purposes and Objectives:

The primary objective of this study is to characterize the carotenoid status of mothers during pregnancy, specifically to determine if prenatal supplementation counteracts maternal systemic and ocular carotenoid depletion.

The primary outcome measure will be change in carotenoid levels from enrollment to final study visit (birth of child) as measured in serum, skin and the macula by high-performance liquid chromatography (HPLC), resonance Raman spectroscopy, and macular pigment imaging, respectively.

7. Is this a multi-site study, where more than one site needs IRB approval?

Yes No

8. Background and Introduction:

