Prenatal vitamin and micronutrient supplementation is standard-of-care for pregnant women worldwide; however, with the exception of a few ingredients, most prenatal supplementation guidelines are not yet supported by substantial prospective clinical research. Recently, prenatal supplements with added lutein and zeaxanthin have entered the American market with the stated intentions of enhancing infant visual and neural development and maintaining maternal health. Although clinical trials were never performed to support these contentions, it is physiologically plausible from the neonate's perspective because these dietary carotenoids are selectively concentrated in human ocular and neural tissue *in utero*, especially during the third trimester of pregnancy.

From the mother's perspective, the last trimester of pregnancy is a time when she must transfer some of her carotenoid stores to the developing infant via the placenta, potentially putting her at risk for depletion systemically and in her ocular tissues. On review of the published literature, there are conflicting data regarding systemic maternal carotenoid status throughout pregnancy, and absolutely nothing is known about maternal macular pigment levels in the eye during pregnancy. Some, but not all, studies report lower serum carotenoid levels in pregnant women. [name] and others (Henriksen et al., 2013; Kiely et al., 1999; Zhang et al., 2001) have reported that mothers who did not take lutein or zeaxanthin supplements during pregnancy had >50% reductions of serum lutein and zeaxanthin concentrations and ~20% lower total skin carotenoids at the time of delivery when compared to our clinic's average of unsupplemented non-pregnant adults.

Prospective, controlled clinical trials to demonstrate the benefits of carotenoid supplementation during pregnancy have never been conducted. To obtain data relative to the feasibility of such trials, this study will be a comprehensive, prospective assessment of prenatal lutein + zeaxanthin supplementation on maternal and infant ocular and systemic biomarkers of carotenoid status throughout pregnancy.

Please see pp. 27- 30 of the protocol for the list of literature cited.

IRB_00116610

Created: 10/1/2018 12:13
PM

IRB_00116610

2. Study Location and Sponsors

PI: [name]

Submitted: 11/21/2018

Title: Lutein & Zeaxanthin in Pregnancy (L-ZIP) -
Carotenoid Supplementation During Pregnancy:
Ocular and Systemic Effects

2. Study Location and Sponsors

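### The 0.90 power is for skin carotenoid level at birth, but the primary outcome is change from enrollment, and no SD of change or correlation is given

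*Combined protocol and SAP*

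**What the plan says.** **Outcome.** In 1. Study Introduction, item 6: "The primary outcome measure will be change in carotenoid levels from enrollment to final study visit (birth of child"). It is measured in serum, skin and the macula.

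**Sizing.** 4. Study Information, item 9, Sample Size Calculation and Power Considerations, begins: "Statistical power and sample size (N) for one of the primary outcome measures, maternal skin carotenoids at birth, was determined using data". The inputs are a mean of 34,000 (SD 8,300) at birth from an earlier study and a clinic average of about 42,500 Raman counts. With power 0.90 and alpha 0.05, "a sample size of 20 was calculated for each group in order to detect and prevent a 20% decline during pregnancy". Enrollment is set at 30 per arm to allow for losses of about 10% and about 20%.

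**Origin of the 20%.** The Background (item 8) describes it as "lower total skin carotenoids at the time of delivery when compared to our clinic's average of unsupplemented non-pregnant adults".

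**Timing of baseline.** In the Study Visit Schedule, "Initial evaluation of each mother's carotenoid status will be obtained prior to starting any study supplements"; the table puts this visit at "Before 14 Wks GA".

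**Other measures.** For a group of outcomes that includes maternal ocular depletion, item 9 says only that "we estimate that a similar sample size of 20 patients per group will be sufficient to detect differences in these indices". On macular pigment, the Background says "absolutely nothing is known about maternal macular pigment levels in the eye during pregnancy". Maternal serum is not mentioned in the sample-size text.

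**Test.** Efficacy Analyses names paired t-tests, two-tailed at 0.05, but describes them as comparing supplemented with unsupplemented mothers. It leaves the full SAP to be finalized before database lock.

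**The concern.** A level at one visit and a change between two visits have different variances unless r happens to be 0.5 (with equal SDs). An SD of 8,300 for the level therefore says nothing about power for change until r, or the SD of change, is supplied. Neither appears in the document.

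The effect size has a related weakness. The 8,500 counts separate women at delivery from a different group of non-pregnant adults. The trial's baseline is taken in women already pregnant, so any part of that gap present by the enrollment visit cannot appear in the measured change. The calculation also assumes that the supplement prevents the whole gap.

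What is at stake is how a null result is read. If r is low, a change-score comparison has clearly less than 0.90 power, and a null skin result would be less informative than the plan implies. For macula and serum there is no power calculation against which to read a null result.

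**Working it through.** **Inputs from the plan.** Mean at birth 34,000, SD 8,300, reference 42,500 (item 9); two-sided 0.05 (Efficacy Analyses). Difference = 42,500 − 34,000 = 8,500, which is 20% of 42,500.

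**1. Reproduce the plan's figure.** No test is named in the sample-size text. For a two-sample comparison of levels:

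n per group = 2(1.960 + 1.2816)² × (8,300/8,500)² = 20.04

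This matches the stated 20. Exact t-test power is 0.884 with 20 per group and 0.899 with 21. A paired or one-sample test with SD 8,300 would need only 13, and a difference of 6,800 (20% of 34,000) would need 32 per group. The two-sample comparison of levels at birth with a difference of 8,500 is the most plausible source.

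**2. Power for change.** Assume SD 8,300 at both visits and in both arms, the same difference, 20 per group, and r from 0 to 0.7. None of these r values comes from the plan.

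SD of change = 8,300 × √(2(1 − r))

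| r | SD of change | Power, 20 per group | n per group for 0.90 |
|---|---|---|---|
| 0 | 11,738 | 0.61 | 42 |
| 0.3 | 9,821 | 0.76 | 30 |
| 0.5 | 8,300 | 0.88 | 22 |
| 0.7 | 6,429 | 0.98 | 14 |

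Power reaches 0.90 at r = 0.526.

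**3. Power for a baseline-adjusted comparison (ANCOVA).** The residual SD is 8,300 × √(1 − r²), with 37 degrees of freedom. The half-difference (4,250) is illustrative. The last column assumes that the supplemented arm's SD keeps the same ratio to its mean: 8,300/34,000 × 42,500 = 10,375. The pooled SD is then √((8,300² + 10,375²)/2) = 9,395, used in place of 8,300.

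| r | Residual SD | Power, 8,500 | Power, 4,250 | Power, 8,500, SD 10,375 in supplemented arm |
|---|---|---|---|---|
| 0 | 8,300 | 0.88 | 0.35 | 0.80 |
| 0.3 | 7,918 | 0.91 | 0.38 | 0.83 |
| 0.5 | 7,188 | 0.95 | 0.44 | 0.90 |
| 0.7 | 5,927 | 0.99 | 0.60 | 0.97 |

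**4. Evaluable number.** Taking off 10% and 20% of 30 together leaves 30 × 0.70 = 21 per arm, so 20 is a fair basis for these figures.

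**The case against.** The strongest reply is that nothing is miscalculated and the mismatch is mild. The stated 20 reproduces. Under randomization the expected between-arm difference is the same for the birth level and for change, so only the variance differs. Sizing on the birth level is then a usable basis for a baseline-adjusted analysis, which the open SAP still permits. The low figures arise only with an unadjusted change-score test at low r, and the plan does not clearly name that test. All of this is right. It is also the reason for recommending ANCOVA, but the plan does not specify ANCOVA.

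A second reply is that the r = 0.53 threshold is fragile. With 21 evaluable it falls to about 0.50, and with 24 to about 0.43. It moves the other way if the enrollment SD is larger: with 10,375 at enrollment and 8,300 at birth, power for change at r = 0.5 is 0.79. This stands. The threshold is illustrative, and its sensitivity confirms that the power for change cannot be fixed from the plan.

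Third, the cross-sectional origin of the 8,500 affects the level comparison too, and ANCOVA does not cure it. That is also true, so the difference must be labeled as assumed and power shown for a smaller one.

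Finally, the plan confines 0.90 to one measure, calls the others less well characterized, and reports serum reductions above 50% in the Background. Confining the figure to skin is to the plan's credit. However, the sufficiency claim for ocular depletion has no calculation behind it, and the serum reduction comes without an SD.

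**Conclusion.** The concern holds. The plan's only power figure belongs to skin carotenoid level at birth and cannot be carried over to change from enrollment, because the variance of change is neither given nor derivable. This is a mismatch between the sizing endpoint and the defined outcome, not an error in computing 20 per group.

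It does not show that the trial is underpowered. With equal SDs of 8,300, a difference of 8,500 and 20 per group, power for change runs from 0.61 at r = 0 to 0.98 at r = 0.7. If the true difference were half as large, even ANCOVA would have only 0.35 to 0.60 over that range. No power has been established for the serum or macular measures. The r values, the equal SDs and the half-difference are assumptions.

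**What to change.** Keep enrollment as planned.

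1. In the SAP, make the between-arm test for skin an ANCOVA of the birth value with the enrollment value as covariate. With that covariate in the model, the arm effect is identical whether the response is the birth value or the change. The sizing endpoint and the item 6 outcome then agree.

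2. Replace the power statement with a conditional one, for example: *With 20 evaluable per group and SD 8,300 in both arms, power for a between-arm difference of 8,500 counts at two-sided 0.05 is about 0.88 with no baseline correlation, and 0.91, 0.95 and 0.99 at r = 0.3, 0.5 and 0.7. For half that difference it is about 0.35, 0.38, 0.44 and 0.60 at r = 0, 0.3, 0.5 and 0.7. If the supplemented-arm SD is 10,375, power for 8,500 is about 0.80 at r = 0. No power is claimed for serum or macular measures.*

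3. Describe 8,500 as an assumed between-arm difference, not as an observed decline during pregnancy.

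**Cost.** This changes the skin analysis, replacing the paired t-test wording, so it is more than an edit of text; the SAP is open until database lock. The power claim becomes conditional and covers one measure. No participants or measurements are added, because the enrollment value is already collected.
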